STUDY TITLE:

**“VALUE OF TEMPORARY OCCLUSION OF THE
UTERINE ARTERIES IN LAPAROSCOPY
MYOMECTOMY”**

INVESTIGATOR: [name] [name]. Head of the Gynecology Section.
Ramon y Cajal Hospital in Madrid.

CENTER: RAMÓN Y CAJAL UNIVERSITY HOSPITAL

Address: [name].

Gynecology Service

Email: [contact]

[contact]

SUMMARY:

1. Objectives:

- Main objective: To analyze the patients who underwent a laparoscopic myomectomy, to assess whether there are significant differences in terms of a decrease in intraoperative blood loss between patients with temporary clamping of the uterine arteries and utero-ovarian ligaments and patients without temporary occlusion during the surgical technique.

- Secondary objectives: To determine the surgical time of each technique, the improvement of the symptoms for which the patient is operated, the length of hospital stay and the possible complications of each technique.

2. Methods:

- **Study design** : This is a randomized prospective longitudinal clinical trial in patients with fibroids who require surgery, from the Gynecology service of the Ramón y Cajal Hospital.

- **Study population and total number of subjects** :

A total of 37 patients who underwent laparoscopic myomectomy with temporary occlusion of the uterine arteries and utero-ovarian ligaments using clips will be analyzed with a control group of 37 patients who underwent laparoscopic myomectomy with the traditional technique (surgery without temporary occlusion of uterine arteries).

The sample size has been calculated based on data published in the literature, where there is a difference in hemoglobin levels of 0.7 g/dl between the two groups, with a statistical power of 80% and an alpha error of 5%.

1. INTRODUCTION.

Uterine fibroids are the most frequent benign tumors originating in smooth muscles of the female genital tract.

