2. GOALS

Main objective :

- To identify the efficacy of temporary occlusion of the uterine arteries during laparoscopic myomectomy by comparing blood loss (by assessing pre- and postoperative hemoglobin in g/dL and intraoperative blood aspirate in milliliters), in 2 groups of patients with symptomatic fibroids undergoing laparoscopic surgery, one with temporary occlusion of uterine arteries and uteroovarian ligaments and one without such occlusion.

Secondary objectives:

- Compare the surgical time of each technique.
- Compare the need for transfusion between both groups.
- Compare the improvement of the symptoms for which the patient is operated.
- Compare the length of hospital stay in each group
- Compare possible complications of each technique.

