3. METHODOLOGY

3.1. DESIGN : Longitudinal prospective randomized clinical trial.

3.2. SUBJECTS OF STUDY : Patients with symptomatic fibroids who require surgery to treat them, from the Gynecology Service of the Ramón y Cajal Hospital. Patients will be randomized into 2 groups: exposed (patients with temporary occlusion of the uterine arteries by clips during surgery) and non-exposed (patients without temporary occlusion of the uterine arteries during surgery).

A patient will be recruited in the pre-surgical consultation when laparoscopic myomectomy is indicated, randomizing both groups by simple random sampling. An informed consent will be delivered to the patients, who have to accept and sign in order to participate in the study. The diagnosis of the presence of fibroids will be made by abdominal and/or transvaginal gynecological ultrasound and/or nuclear magnetic resonance. Fibroids will be quantified, measured and their location described.

3.3. INCLUSION CRITERIA : The inclusion criteria to participate in the study are the existence of uterine fibroids with an indication for laparoscopic surgery and the patient's desire to preserve the uterus.

3.4. EXCLUSION CRITERIA : Patients who do not meet the inclusion criteria, women with symptomatic fibroids who are not candidates for laparoscopic surgery and/or do not

wish to preserve the uterus, those patients who, despite having indications for randomization, do not have the technical possibility of clipping during the intervention.

3.5. VARIABLES TO STUDY : The patients included in the study will have their pre-surgical hemoglobin determined by preoperative analysis and another post-surgical hemoglobin sample will be determined the day after surgery. The need for transfusion, blood loss during surgery (aspirate the blood content), surgical time, hospital stay, symptom improvement and complications will be assessed.

In addition, clinical data on the patients will be collected: age, height, weight, race, concomitant diseases and treatment, family history, age at menarche, tobacco and alcohol consumption, main clinic where the surgery is performed.

3.6. INFORMATION SOURCES :

To obtain the necessary information from the study, the HCIS medical records will be used.

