3.7. STATISTICAL ANALYSIS OF THE DATA

The data collected from the medical records will be tabulated in a main database with the SPSS version 23.0 program (IBM Corp. Released 2008. IBM SPSS Statistics for Windows, version 23.0 Armonk , NY: IBM Corp) For the statistical analysis, the same program will be used. The time for patient recruitment and data collection can be estimated at one year.

The absolute and relative frequency distributions of the qualitative variables will be presented.

The differences in the values of the quantitative variables will be studied using the most appropriate test in each case, Student 's t test to compare two groups and the corresponding non-parametric ones.

In the analysis of the contingency tables for qualitative variables and their possible association between them, Pearson's chi-square test will be used.

In all the analyzes the level of statistical significance is considered with a minimum probability of 95% ($p < 0.05$).

4 . ETHICAL AND LEGAL ASPECTS

The study will be governed by the basic ethical principles contained in the Declaration of Helsinki (*WORLD MEDICAL ASSOCIATION DECLARATION OF HELSINKI. Ethical principles For Medical Research Involving Human Subjects . Adopted by the 18th WMA General Assembly Helsinki, Finland , June 1964 and amended by the 29th WMA General Assembly , Tokyo , Japan , October 1975; 35th WMA General Assembly , Venice , Italy , October 1983; 41st WMA General Assembly , Hong Kong, September 1989; 48th WMA General Assembly , Somerset West, Republic of South Africa , October 1996 and; the 52nd WMA General Assembly , Edinburgh, Scotland, October 2000 and note of clarification on paragraph 29 added by the WMA General Assembly , Washington 2002 and its amendments of 2004, 2008 and 2013*), in the Guide to Good Clinical Practices in Human Health Research, in LAW 14/2007, of July 3, on Biomedical Research, published in BOE No. 159 of Wednesday, July 4, 2007, in the Agreement for the Protection of Human Rights and the Dignity of the Human Being with respect to the Applications of Biology and Medicine, drawn up in Oviedo on April 4, 1997 and signed on July 23, 1999, and accepted by the Biomedical Research Law 14/2007. In accordance with said agreement, the data obtained will never be used for profit (article 21) and may not be used for a purpose other than that for which it is reported in this document (article 22).

4.1. CONFIDENTIALITY OF THE DATA.

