The highest levels of professional conduct and confidentiality will always be maintained and the current national legislation on data protection of 2018 will be complied with (General Data Protection Regulation -RGPD- and Organic Law Organic Law on Data Protection and Guarantee of Digital Rights - LO 3/2018 PD and GDD-). Only those data from the clinical history that are related to the study will be subject to verification. The patients' right to confidentiality will be respected. For this, the information of the study subjects will be dissociated using codes. Access to your personal information will be restricted to the study doctor and his collaborators, health authorities and Research Ethics Committee, who will be subject to the duty of secrecy inherent to their profession, when necessary, to verify the study data and procedures, but always maintaining their confidentiality in accordance with current legislation . The identity of the patients will be coded in the documents used for the study data collection by means of a number that will be used (obviously omitting the name and/or other affiliation data that could identify the patient) and only duly authorized personnel will have access to the identifiable personal data when the data verification procedures require inspection of that information . Personal details that could identify the patient will always be kept confidential.

In compliance with current regulations, approval will be obtained from the Hospital's Clinical Research Ethics Committee, so that your rights and level of care are always guaranteed.

4.2. INFORMED CONSENT.

All patients who are going to undergo a laparoscopic myomectomy will be offered the possibility of participating in the study and if they accept, the relevant consent to the surgery will be delivered, approved by the SEGO Ethics Committee, which refers to the myomectomy procedure; an information sheet and a specific consent that has been designed exclusively for this study and which is attached in annex I.

5. WORK PLAN:

- 5.1. Study schedule:** from the approval of the study by the CEIC to completion of the recruitment of the established sample size. Approximately one year of time is estimated.

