- 5.2. Patient recruitment:** Patients will be recruited in the pre-surgical consultation, when laparoscopic myomectomy is indicated, randomizing both groups by simple random sampling. An informed consent will be delivered to the patients, who have to accept and sign in order to participate in the study. Fibroids will be quantified, measured and their location described.
- 5.3. Performing the surgical act:** during the laparoscopic myomectomy, temporary occlusion of the uterine arteries will be carried out using clips in those patients who are assigned to the exposed group.
- 5.4. Data collection: the pre-surgical hemoglobin determination** will be collected through the preoperative analysis and another post-surgical hemoglobin sample will be determined the day after surgery. The need for transfusion, blood loss during surgery (aspirate the blood content), surgical time, hospital stay, symptom improvement and complications will be assessed ; in addition to clinical data of the patients.
- 5.5. Statistical analysis of the collected data.**

6. BIBLIOGRAPHICAL REFERENCES:

3: Bedaiwy MA. Uterine artery occlusion at myomectomy? Towards a better definition of the indications. *Fertile Sterile* . 2019 Apr;111(4):685-686. doi : 10.1016/j.fertnstert.2019.01.024. Epub 2019 Mar 8. PubMed PMID: 30853090.

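### Section 3.4 excludes, after randomisation, patients who cannot be clipped at operation; this probably empties the clip arm only and can bias the blood-loss comparison

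*Combined protocol and SAP*

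**What the plan says.** Randomisation comes before surgery. Section 3.2: "A patient will be recruited in the pre-surgical consultation when laparoscopic myomectomy is indicated, randomizing both groups by simple random sampling". Section 5.2 repeats it in the work plan.

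Section 3.4 lists among the exclusions "those patients who, despite having indications for randomization, do not have the technical possibility of clipping during the intervention". It names no arm, does not define technical possibility, and does not say when or by whom it is judged.

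Section 5.3 says that "temporary occlusion of the uterine arteries will be carried out using clips in those patients who are assigned to the exposed group". No section describes a matching assessment in controls.

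Section 3.7 gives the tests: "The differences in the values of the quantitative variables will be studied using the most appropriate test in each case", namely Student's t test or a non-parametric equivalent, and chi-square for categorical data. It defines no analysis population and no rule for a patient allocated to clips who did not receive them. The Summary describes the clip group this way: "A total of 37 patients who underwent laparoscopic myomectomy with temporary occlusion of the uterine arteries and utero-ovarian ligaments using clips will be analyzed". That is loose wording; it neither sets nor excludes an analysis by treatment received.

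**The concern.** Randomisation makes the two groups comparable at the moment of allocation. A rule that then removes patients for something learned in theatre keeps that comparability only if it removes the same kind of patient from both arms. Here feasibility is revealed where clipping is attempted, which is the clip arm. An unclippable control would not be identified and would stay in, so clippable patients would be compared with a mixture of clippable and unclippable ones.

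If unclippable women bleed more than the rest, the comparison favours clipping. If they bleed less, it goes against clipping. If they bleed the same, there is no bias under the null hypothesis. The protocol does not ask for failed clippings to be recorded, so the bias could be neither bounded nor corrected afterwards. Surgical time and complications would be compared in the same altered groups, and any time or complications caused by a failed attempt would drop out; that effect was not computed.

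**Working it through.** **Order of events.** Consultation and randomisation (3.2, 5.2), then operation with clips in the exposed group only (5.3), then exclusion if clipping proves impossible (3.4), then analysis with no stated population (3.7). The exclusion follows allocation. That it acts on one arm is an inference from 5.3, not a written rule.

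**Inputs from the documents (Summary).** 37 per arm, a haemoglobin difference of 0.7 g/dL, 80% power, 5% alpha. No standard deviation (SD), sidedness or allowance for exclusions is stated.

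**The plan's own figure.** Without an SD, 37 per arm cannot be reproduced, only back-solved. With a two-sided 5% t test, power is 80% at n = 37 and 0.7 g/dL when SD = 1.06 g/dL (noncentral t). One-sided, the SD would be about 1.20. I use 1.06.

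**Assumptions.** q is the share unclippable, and D is their extra haemoglobin drop in g/dL. The 0.7 is read as a difference in haemoglobin drop. 1.06 is the overall SD in controls. 37 are analysed per arm, so excluded patients are taken to be replaced.

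**Bias with no true effect.** Let m be the mean drop in clippable patients. The control mean is m + qD and the clip-arm mean after exclusion is m, so bias = q × D.

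- q = 10%, D = 1: 0.10 × 1 = 0.10 g/dL, which is 0.10/0.70 = 14% of the target.
- q = 20%, D = 1: 0.20 × 1 = 0.20 g/dL, which is 29% of the target.

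**Type I error.** The variance within the clippable and unclippable groups is 1.06² − q(1−q)D². For q = 20%, D = 1 this is 1.1236 − 0.16 = 0.9636. The standard error is √((0.9636 + 1.1236)/37) = 0.2375, so the shift is 0.20/0.2375 = 0.84 standard errors. The two-sided rejection rate is then about 13%. Other cases in the same way:

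| q | D (g/dL) | Bias (g/dL) | Type I error, clip-arm exclusion |
|---|---|---|---|
| 5% | 0.5 | 0.025 | 5.1% |
| 5% | 1 | 0.05 | 5.5% |
| 10% | 0 | 0 | 5.0% |
| 10% | 0.5 | 0.05 | 5.5% |
| 10% | 1 | 0.10 | 6.9% |
| 10% | −1 | −0.10 | 6.9%, against clipping |
| 20% | 0.5 | 0.10 | about 7% |
| 20% | 1 | 0.20 | 13% |

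Simulation (200,000 runs per case) agrees within a few tenths of a percentage point. Analysed as allocated, the simulated rate is 4.9–5.1% throughout.

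**What analysis as allocated costs in power.** If unclippable patients get no benefit, the effect is 0.7 × (1 − q): 0.63 g/dL at q = 10% and 0.56 at q = 20%. The clip-arm variance is the within-group variance plus q(1−q)(D + 0.7)². For q = 10%, D = 1: 1.0336 + 0.09 × 2.89 = 1.2937. The standard error is √((1.2937 + 1.1236)/37) = 0.2556, so 0.63/0.2556 = 2.46 and power is about 68%. At 37 per arm, power is about 68–70% at q = 10% and 56–60% at q = 20% (D from 1 to 0). If 1.06 is instead the SD within the clippable and unclippable groups, power at D = 1 is 65% and 51%.

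**The case against.** The strongest objection is to the reading. In 3.4, the reference to the intervention may describe the clipping rather than the time at which feasibility is judged. The criterion stands in an eligibility list, and 3.2 has the fibroids counted, measured and located by imaging, so a judgement before randomisation is conceivable. If that is meant, the problem does not arise. But 3.4 speaks of patients who otherwise qualify for randomisation, and nothing in 3.2 or 5.2 places a feasibility check before allocation. The post-randomisation reading is the more natural one, and under either reading the text needs to change.

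That the exclusion acts on one arm is indeed inferred, and is stated here only as probable.

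The figures are also open to challenge, and fairly. The larger ones rest on D = 1 g/dL, which exceeds the whole 0.7 target; at D = 0.5 the error rate reaches only about 7% even at q = 20%. Without replacement of excluded patients (33 or 30 against 37), the D = 1 results are about 6.7% and 12%. With replacement, about 41 or 46 would be randomised to clips (37/0.9 and 37/0.8). As-allocated power with those numbers in each arm, at D = 1, is about 72% and 65%, so the loss charged to the fix above is then too large. Only haemoglobin is illustrated, not aspirated volume. These points change the illustrations, not the conclusion.

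A sponsor may reply that the interest lies only in women who can be clipped. That question needs controls who could also have been clipped, and the present rule does not supply them.

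**Conclusion.** The concern holds. Followed as written, the plan removes patients after allocation, probably from the clip arm only, and nothing in section 3.7 restores them. The primary comparison then loses the protection of randomisation, which is why this must be fixed before data are seen.

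The size of the bias is unknown. It is negligible at a 5% failure rate and could matter at 20%: 0.20 g/dL and a type I error of about 13% under D = 1, SD 1.06 and a two-sided test. q, D and the SD are all assumptions, and the direction reverses if D is negative. The severity rests on the broken comparison, not on these figures.

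**What to change.** 1. State in 3.4 when feasibility of clipping is judged. If it is judged from imaging before randomisation, say so, and the matter is closed.
2. Otherwise remove the criterion as a reason for exclusion after randomisation.
3. Add to 3.7: *The primary analysis includes every randomised and operated patient in the group to which she was allocated, including patients allocated to clips in whom clips were not placed.* State separately how randomised women who are not operated on, or who lack a postoperative haemoglobin, are counted and handled.
4. Record each failed clipping with its reason. Report the clipped-only comparison as a sensitivity analysis, labelled as not protected by randomisation.
5. Reword the Summary to speak of 37 patients allocated to each technique.
6. State the assumed clipping-failure rate and restate power with it.

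Randomising only after feasibility has been judged identically in every patient is an alternative for the sponsor to weigh; it would add an intraoperative step in controls that the protocol does not describe.

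The cost is wording plus one recorded item, and the loss of power shown above. Keeping 37 per arm and stating the lower power is sufficient. For information, holding 80% power would take about 42–43, 47–49 or 60–65 per arm at q = 5%, 10% or 20%. At the planned pace of 74 patients in the period given in 5.1 ("Approximately one year of time is estimated"), that is n × 2/74 × 12, or roughly 14, 15–16 or 19–21 months.

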3.7. STATISTICAL ANALYSIS OF THE DATA

The data collected from the medical records will be tabulated in a main database with the SPSS version 23.0 program (IBM Corp. Released 2008. IBM SPSS Statistics for Windows, version 23.0 Armonk , NY: IBM Corp) For the statistical analysis, the same program will be used. The time for patient recruitment and data collection can be estimated at one year.

The absolute and relative frequency distributions of the qualitative variables will be presented.

The differences in the values of the quantitative variables will be studied using the most appropriate test in each case, Student 's t test to compare two groups and the corresponding non-parametric ones.

In the analysis of the contingency tables for qualitative variables and their possible association between them, Pearson's chi-square test will be used.

In all the analyzes the level of statistical significance is considered with a minimum probability of 95% ($p < 0.05$).

4 . ETHICAL AND LEGAL ASPECTS

The study will be governed by the basic ethical principles contained in the Declaration of Helsinki (*WORLD MEDICAL ASSOCIATION DECLARATION OF HELSINKI. Ethical principles For Medical Research Involving Human Subjects . Adopted by the 18th WMA General Assembly Helsinki, Finland , June 1964 and amended by the 29th WMA General Assembly , Tokyo , Japan , October 1975; 35th WMA General Assembly , Venice , Italy , October 1983; 41st WMA General Assembly , Hong Kong, September 1989; 48th WMA General Assembly , Somerset West, Republic of South Africa , October 1996 and; the 52nd WMA General Assembly , Edinburgh, Scotland, October 2000 and note of clarification on paragraph 29 added by the WMA General Assembly , Washington 2002 and its amendments of 2004, 2008 and 2013*), in the Guide to Good Clinical Practices in Human Health Research, in LAW 14/2007, of July 3, on Biomedical Research, published in BOE No. 159 of Wednesday, July 4, 2007, in the Agreement for the Protection of Human Rights and the Dignity of the Human Being with respect to the Applications of Biology and Medicine, drawn up in Oviedo on April 4, 1997 and signed on July 23, 1999, and accepted by the Biomedical Research Law 14/2007. In accordance with said agreement, the data obtained will never be used for profit (article 21) and may not be used for a purpose other than that for which it is reported in this document (article 22).

4.1. CONFIDENTIALITY OF THE DATA.

The highest levels of professional conduct and confidentiality will always be maintained and the current national legislation on data protection of 2018 will be complied with (General Data Protection Regulation -RGPD- and Organic Law Organic Law on Data Protection and Guarantee of Digital Rights - LO 3/2018 PD and GDD-). Only those data from the clinical history that are related to the study will be subject to verification. The patients' right to confidentiality will be respected. For this, the information of the study subjects will be dissociated using codes. Access to your personal information will be restricted to the study doctor and his collaborators, health authorities and Research Ethics Committee, who will be subject to the duty of secrecy inherent to their profession, when necessary, to verify the study data and procedures, but always maintaining their confidentiality in accordance with current legislation . The identity of the patients will be coded in the documents used for the study data collection by means of a number that will be used (obviously omitting the name and/or other affiliation data that could identify the patient) and only duly authorized personnel will have access to the identifiable personal data when the data verification procedures require inspection of that information . Personal details that could identify the patient will always be kept confidential.

In compliance with current regulations, approval will be obtained from the Hospital's Clinical Research Ethics Committee, so that your rights and level of care are always guaranteed.

4.2. INFORMED CONSENT.

All patients who are going to undergo a laparoscopic myomectomy will be offered the possibility of participating in the study and if they accept, the relevant consent to the surgery will be delivered, approved by the SEGO Ethics Committee, which refers to the myomectomy procedure; an information sheet and a specific consent that has been designed exclusively for this study and which is attached in annex I.

5. WORK PLAN:

- 5.1. Study schedule:** from the approval of the study by the CEIC to completion of the recruitment of the established sample size. Approximately one year of time is estimated.
- 5.2. Patient recruitment:** Patients will be recruited in the pre-surgical consultation, when laparoscopic myomectomy is indicated, randomizing both groups by simple random sampling. An informed consent will be delivered to the patients, who have to accept and sign in order to participate in the study. Fibroids will be quantified, measured and their location described.
- 5.3. Performing the surgical act:** during the laparoscopic myomectomy, temporary occlusion of the uterine arteries will be carried out using clips in those patients who are assigned to the exposed group.
- 5.4. Data collection: the pre-surgical hemoglobin determination** will be collected through the preoperative analysis and another post-surgical hemoglobin sample will be determined the day after surgery. The need for transfusion, blood loss during surgery (aspirate the blood content), surgical time, hospital stay, symptom improvement and complications will be assessed ; in addition to clinical data of the patients.
- 5.5. Statistical analysis of the collected data.**

6. BIBLIOGRAPHICAL REFERENCES:

3: Bedaiwy MA. Uterine artery occlusion at myomectomy? Towards a better definition of the indications. *Fertile Sterile* . 2019 Apr;111(4):685-686. doi : 10.1016/j.fertnstert.2019.01.024. Epub 2019 Mar 8. PubMed PMID: 30853090.

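### The haemoglobin comparison is planned only as an unadjusted t or rank test; adjusting for the pre-surgical haemoglobin already recorded would usually give a narrower interval and more power at almost no cost

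*Combined protocol and SAP*

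**What the plan says.** Section 3.7 (Statistical analysis of the data) says the most suitable test will be chosen in each case for quantitative variables, then names "Student 's t test to compare two groups and the corresponding non-parametric ones". Pearson's chi-square is named for qualitative variables. No regression, ANCOVA, stratified analysis or covariate is mentioned anywhere in the text supplied.

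The baseline data exist. Under section 3.5, included patients "will have their pre-surgical hemoglobin determined by preoperative analysis and another post-surgical hemoglobin sample will be determined the day after surgery". Sections 3.2 and 5.2 add: "Fibroids will be quantified, measured and their location described". Allocation is described as "randomizing both groups by simple random sampling", with no stratification.

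The form of the Hb outcome is left open. The main objective in section 2 assesses blood loss "by assessing pre- and postoperative hemoglobin in g/dL and intraoperative blood aspirate in milliliters". The sample-size paragraph of the Summary says only that "there is a difference in hemoglobin levels of 0.7 g/dl between the two groups".

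**The concern.** With 74 patients and simple randomisation, an unadjusted comparison leaves in the error term all the variation in day-after Hb that pre-surgical Hb could explain. It also makes no correction for chance imbalance in baseline Hb. The confidence interval is then wider, and power lower, than the collected data would allow. The sample size rests on 80% power with no stated allowance for dropout, so there is little reserve.

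The undefined outcome adds to this. A t test on the change and a t test on the postoperative value can differ widely in power, and leaving the choice open allows it to be made after the data are seen.

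**Working it through.** **Inputs from the plan (Summary):** 37 per arm, difference 0.7 g/dl, power 80%, alpha 5%.

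**Assumptions, because the plan gives no figure:** two-sided test; no dropout; equal pre and post variances; pre/post correlation ρ from 0.3 to 0.9; SD as back-solved in step 1.

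**1. The plan's own figure.** Without an SD, 37 per arm cannot be reproduced; the SD can only be back-solved.
- Normal approximation: SD = 0.7 / [(1.960 + 0.842) × √(2/37)] = 1.075.
- Noncentral t on 72 df: SD = 1.060, used below. A one-sided test would imply about 1.21 (normal approximation).

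**2. Unadjusted precision.** SE = 1.060 × √(2/37) = 0.2465. The 95% half-width is 1.9935 × 0.2465 = 0.491 g/dl, with 80% power.

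**3. Effect of adjusting for baseline Hb.** Relative to a postoperative variance of 1, the change has variance 2(1−ρ) and the ANCOVA residual has 1−ρ². The variance ratio (VR) of ANCOVA to the unadjusted test is therefore
- (1−ρ²) / [2(1−ρ)] = (1+ρ)/2 if the planned test is on the change;
- 1−ρ² if it is on the postoperative value.

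Power is from the noncentral t on 71 df with SD 1.060 × √VR. Half-width is 1.9939 × 0.2465 × √VR.

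| ρ | Change: VR | Power | Half-width | Postoperative: VR | Power | Half-width |
|---|---|---|---|---|---|---|
| 0.3 | 0.65 | 93.5% | 0.396 | 0.91 | 83.6% | 0.469 |
| 0.5 | 0.75 | 89.9% | 0.426 | 0.75 | 89.9% | 0.426 |
| 0.7 | 0.85 | 86.0% | 0.453 | 0.51 | 97.5% | 0.351 |
| 0.9 | 0.95 | 82.0% | 0.479 | 0.19 | >99% | 0.214 |

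In the left half 1.060 is the SD of the change; in the right half it is the SD of the postoperative value.

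**4. Simulation with the slope estimated** (20,000 trials per scenario):
- Change, ρ 0.5/0.7/0.9: 89.2%, 85.8%, 81.2%.
- Postoperative, ρ 0.3/0.5/0.7: 82.9%, 89.7%, 97.3%.
- With two further covariates that predict nothing: 88.4%, 84.7%, 80.2% and 81.8%, 88.9%, 97.0%. Useless covariates thus cost about 1 point.

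**5. Why the outcome must be defined.** If 1.060 is the SD of the postoperative value, a t test on that value has 80% power. A t test on the change has about 66%, 80% or 95% at ρ 0.3, 0.5 or 0.7. Since 1−ρ² = (1−ρ)(1+ρ) exceeds neither 1 nor 2(1−ρ), the ANCOVA residual variance is never above that of either unadjusted test under these assumptions.

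**6. Chance imbalance.** Under the postoperative reading, baseline Hb has the same SD, so the between-arm baseline difference has SE 0.2465, about 0.25 g/dl. A difference at least that large would occur in about one trial in three. Against a 0.7 g/dl target that is not trivial, and a test on the postoperative value ignores it.

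**The case against.** The planned test is valid and, on the trial's own calculation, has 80% power; no conclusion becomes wrong if nothing changes. That stands, and the point is put as lost efficiency only.

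The change is the more natural reading of section 2, since postoperative Hb alone does not measure loss. Baseline is then already partly used, and the largest gains above do not apply. This also stands: the left half of the table is the safer guide. At ρ = 0.9 with two uninformative fibroid covariates the simulated power is 80.2%, so the benefit is essentially cancelled; at ρ = 0.95 it is about 79%, a slight loss. The gain is therefore not guaranteed, and the fibroid covariates should be few or omitted.

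The SD, correlation, equal variances and two-sidedness are all assumed. This limits what can be said about size, but not the fact that no adjustment is planned.

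The freedom in section 3.7 to choose the most suitable test might be read as allowing ANCOVA. It does not supply it: every test then named is unadjusted, and a model chosen after seeing the data would not be prespecified.

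Finally, baseline Hb addresses only the Hb half of the main objective. Aspirated volume has no baseline counterpart, so the remedy is partial.

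**Conclusion.** The concern holds. The plan records a natural baseline covariate for its Hb outcome and does not prespecify its use. Under the assumptions above, adjusting for baseline Hb moves power from 80% to between about 82% and 90% on the change reading for ρ from 0.9 down to 0.5, and the half-width from 0.49 to between 0.48 and 0.43 g/dl. On the postoperative reading, for ρ from 0.3 to 0.7, power is about 84% to 97.5% and the half-width 0.47 to 0.35 g/dl. Any further gain from fibroid covariates is plausible but cannot be quantified from the documents. The existence of the omission is certain; its size is not. This is a worthwhile improvement rather than a flaw that threatens validity.

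**What to change.** In section 3.7, prespecify the primary Hb analysis as a linear model (ANCOVA) of day-after Hb on allocated group with pre-surgical Hb as covariate. One or two fibroid covariates, such as largest diameter and number, may be added if named in advance. Report the adjusted mean difference with its 95% confidence interval. Keep the unadjusted t test as a sensitivity analysis and state whether it is on the change or on the postoperative value. State in the sample-size paragraph which of these the 0.7 g/dl refers to, and the SD used.

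The cost is a few sentences. No new data or patients are needed, and SPSS, already named in section 3.7, fits the model. One to three degrees of freedom are spent. If every covariate proved uninformative, power would fall by about 0.6 points with one covariate and 1.8 with three.
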